Multiple imputation techniques will be applied in the ITT analysis set. For subjects with intermittent missing values, a monotone missingness pattern will be generated. Intermittent missing values will be imputed using the MCMC methodology which assumes a multivariate normal distribution over all variables included in the imputation model. The MI procedure in SAS will be used for this purpose and this first MI step will be repeated 500 times, generating 500 different datasets. A random seed value will be used in the MI procedure and documented in this SAP, to allow replication of the analysis. Seed value of 2002 will be used. The imputation is based on the MAR assumption, i.e., the missing data are assumed to follow the same model as the other subjects in their respective treatment arm. Age, baseline NIHSS, and baseline ASPECTS are included as a factor in the model because the randomization is stratified by these factors. Baseline infarct volume and 48 hour infarct volume will be log transformed prior to imputation. The following SAS code will be used to generate the missing data pattern:

[REDACTED]

If any of the treatment levels has no missing data, the data from the treatment level in question will be excluded from the PROC MI procedure above (using WHERE statement). If this is done, the observed data from the treatment level in question (without any missing data) will be added to the output dataset produced above 500 times, i.e. once for each round of imputation.

Step 2: Imputation of missing data with assumption of MAR

Using the dataset generated in Step 1, all remaining missing values will be imputed based on the assumption of MAR. The following SAS code will be used for the imputation assuming MAR.

[REDACTED]

Step 3: Setting monotone missing data that are not due to COVID-19 back as missing

After Step 2, information on reason for missing data (by subject and visit) will be merged to the dataset that contains no missing data. Within each subject, data from the visits that have monotone missing data that are not due to COVID-19 will be set back as missing for subjects in the active arms.

Step 4: Imputation of missing data with assumption of MNAR

The dataset generated in Step 3 will be imputed based on the assumption of MNAR, using Copy-Reference imputation. The MNAR imputation will be based on the placebo group, i.e. data from the placebo group only will be used to generate the imputations. For this, the MNAR statement will be used as described below.

<

KEY SENSITIVITY ANALYSIS (analysis assuming MNAR)

The analysis consists of the following steps:

1. Imputation of all intermittent missing data with MI assuming MAR, in order to generate a dataset with monotone missing data structure.
2. Based on dataset generated in Step 1: imputation of all monotone missing data with MI assuming MAR, in order to generate dataset with no missing data
3. Based on dataset generated in Step 2 (with no missing data): all visits that have monotone missing data that are not due to COVID-19 will be set back as missing for subjects in the active arms
4. Based on dataset generated in Step 3: imputation of remaining monotone missing data (not related to COVID-19) with multiple imputation assuming MNAR (Copy-Reference imputation)
5. Based on dataset generated in Step 4, analysis of imputed data with GLMs
6. Combination of results from the GLMs.

Step 1: Imputation of intermittent missing data

Multiple imputation techniques will be applied in the ITT analysis set. For subjects with intermittent missing values, a monotone missingness pattern will be generated. Intermittent missing values will be imputed using the Markov Chain Monte Carlo (MCMC) methodology which assumes a multivariate normal distribution over all variables included in the imputation model. The MI

procedure in SAS will be used for this purpose and this first MI step will be repeated 500 times, generating 500 different datasets. A random seed value will be used in the MI procedure and documented in this SAP, to allow replication of the analysis. Seed value of 2003 will be used. The imputation is based on the MAR assumption, i.e., the missing data are assumed to follow the same model as the other subjects in their respective treatment arm. Age, NIHSS, and ASPECTS are included as a factor in the model because the randomization is stratified by these factors. The following SAS code will be used to generate the missing data pattern:

[REDACTED]

If any of the treatment levels has no missing data, the data from the treatment level in question will be excluded from the PROC MI procedure above (using WHERE statement). If this is done, the observed data from the treatment level in question (without any missing data) will be added to the output dataset produced above 500 times, i.e. once for each round of imputation.

Step 2: Imputation of missing data with assumption of MAR

Using the dataset generated in Step 1, all remaining missing data will be imputed based on the assumption of MAR. The following SAS code will be used for the imputation assuming MAR.

[REDACTED]

Step 3: Setting monotone missing data that are not due to COVID-19 back as missing

After Step 2, information on reason for missing data (by subject and visit) will be merged to the dataset that contains no missing data. Within each subject, data from the visits that have monotone missing data that are not due to COVID-19 will be set back as missing for subjects in the active arms.

Step 4: Imputation of missing data (non COVID-19 related) with assumption of MNAR

The dataset generated in Step 3 will be imputed based on the assumption of MNAR, using Copy-Reference imputation. The MNAR imputation will be based on the placebo group, i.e., data from the placebo group only will be used to generate the imputations. For this, the MNAR statement will be used as described below.

[REDACTED]

Step 5: Analysis of imputed data with GLM

The imputed datasets generated in Step 4 do contain only non-missing values and are used as input in the statistical model. RSPL based GLMs will be run on each of the 500 generated imputed datasets. For additional details on how to specify the GLM, see the analysis section corresponding with this sensitivity analysis.

Step 6: Combination of results from the GLMs

Finally, the MIANALYZE procedure in SAS will be applied to combine the 500 results from the analyses generated in Step 3, to derive an estimate of the treatment difference at hour 24. In addition to the estimate, corresponding two-sided 95% CIs and p-values will be generated with the MIANALYZE procedure.

Additionally, neurological functioning at Day 90 will be examined by NIHSS scores at Day 90 between the three treatments (RNS60 1.0 mL/kg/h, RNS60 0.5 mL/kg/h, and placebo 1.0 mL/kg/h). GLM analysis and missing data imputation analysis at Day 90 will be performed using the same approach described above for neurological functioning using 24-hour NIHSS scores.

4. The proportion of subjects with worsening of stroke over the 48-hours/duration of admission:

Worsening of stroke is defined (i.e., Yes or No) as: progression, or hemorrhagic transformation, of the index stroke as documented by medical imaging and that is (a) life-threatening requiring intervention and/or (b) results in increased disability as gauged by a \geq 4-point increase from lowest NIHSS pre decline and/or (c) results in death. Subjects with worsening of stroke will be identified based on a \geq 4-point increase in their worst minus best NIHSS score and adverse events status (life threatening requiring intervention or death) as collected in the CRFs.

The simple effect of treatment on worsening stroke at 48 hours/admission duration will be examined by comparing the proportion of subjects who had worsening stroke (Yes or No) between the three treatments (RNS60 1.0 mL/kg/h, RNS60 0.5 mL/kg/h, and placebo 1.0 mL/kg/h) using GLM using residual pseudo-likelihood with a subject-specific expansion (RSPL) assuming a binary distribution. Covariates include the Age, baseline NIHSS, and baseline ASPECTS as binary factors used for block urn randomization, log of baseline infarct volume, baseline perfusion status, baseline occlusion location, and study site.

The predicted probability for each treatment group and LS mean difference between high-dose and placebo and low-dose and placebo groups along with the 95% CIs will be provided using the LSMEANS/DIFF statement. The comparison of the two combined active arms versus placebo will be performed using the LSMESTIMATE statement with the ILINK option. The odds ratio will also be calculated. The P-value for the hypothesis testing will also be provided. Treatment difference will be assessed with a 2-sided alpha level of 0.05.

The sample SAS code planned for the analysis is outlined below.

5. Barthel Index.

The effect of treatment on functional independence at Day 90 will be examined by comparing subjects achieving functional independence (Barthel Index score ≥ 95 as compared to < 95) where subjects having a score ≥ 95 on the Barthel Index Score at Day 90 will be deemed to have achieved functional independence, and those scoring < 95 at Day 90 will be deemed to have failed to achieve functional independence.

The proportion of subjects who achieved functional independence (BI score ≥ 95 vs. < 95) at Day 90 will be compared between the three treatments (RNS60 1.0 mL/kg/h, RNS60 0.5 mL/kg/h, and placebo 1.0 mL/kg/h) using generalized linear mixed modeling using RSPL assuming a binary outcome ($< 95 = 0$, $\geq 95 = 1$). Covariates include the Age, baseline NIHSS, and ASPECTS binary factors used for block urn randomization and baseline BI total, log of baseline infarct volume, baseline perfusion status, baseline occlusion location, and study site. Treatment, visit day, and interaction of treatment and visit day are included as categorical fixed effects.

Sensitivity analysis of BI will be performed in a similar way to the primary analysis using the GLM approach with RSPL assuming a binary outcome ($<95=0$, $\geq 95=1$) where any missing value of BI will be imputed as functional independence not achieved (coded as 0).

3.4.3 Sensitivity Analysis for Secondary Efficacy Endpoints with Dichotomous Data for Baseline Collaterals

For each of the secondary efficacy endpoints described in section 3.4.2, additional sensitivity analysis will be performed using the GLM analysis approach where baseline collaterals will also be included in the model. For subjects with a baseline collateral score, the score will be converted to baseline collateral status. Baseline collaterals dichotomization will use the following conversion approach:

Dichotomization A (main): where a baseline collateral score of 0-2 indicates Baseline collateral status = Absent, and a baseline collateral score of 3-5 indicates Baseline collateral status = Present

Dichotomization B: where a baseline collateral score of 0 indicates Baseline collateral status = Absent, and a baseline collateral score of 1-5 indicates Baseline collateral status = Present.

Dichotomization C: where a baseline collateral score of 0-1 indicates Baseline collateral status = Absent, and a baseline collateral score of 2-5 indicates Baseline collateral status = Present.

Each efficacy endpoint will be analyzed separately using the GLM model with the main dichotomization A approach included in the model. The SAS code for PROC GLIMMIX in section 3.4.2 will be modified to generate LS Means, LS Means Difference, 95% CIs, and odds ratio (as applicable). Separate GLM analysis with dichotomization B or dichotomization C may also be performed.

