3.1.2 Secondary Objectives

The secondary objectives are to evaluate the efficacy of RNS60 in:

- 1) Reducing global disability
- 2) Reducing mortality rate
- 3) Improving neurological outcome
- 4) Reducing worsening of stroke*
- 5) Reducing functional dependence

* Worsening of stroke is defined as progression, or hemorrhagic transformation, of the index stroke as documented by medical imaging and that is (a) life-threatening requiring intervention and/or (b) results in increased disability as gauged by a ≥ 4 -point increase from lowest NIHSS pre decline and/or (c) results in death.

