3.2.2 Secondary Efficacy Outcomes

Secondary outcomes include:

- 1) The mean mRS score at Day 90, where a lower score is better.
- 2) A reduction in mortality rate, as defined by a lower event rate on a Kaplan Meier survival curve
- 3) The mean NIHSS score post randomization, where a lower score is better
- 4) The proportion of patients with worsening of stroke over the 90-day study period
- 5) The mean BI at Day 90

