	
DWI volume and T2 will be modeled between conditions using generalized linear modeling assuming a normal or lognormal distribution (where appropriate) with sandwich estimation, where observations are nested by site and participant (when appropriate). Pairwise comparisons at post EVT, 48 hours (or early discharge), and 90 days. Simple and interaction effects will be examined across these three timepoints. Because superiority over placebo and lower dose is hypothesized, testing will reflect this superiority framework with one-tailed tests.
 
Because the main aim of this trial is to examine safety, efficacy analysis results are intended to yield estimates to inform powering for subsequent efficacy trial. Alpha is established at the 0.05 level and all interval estimates will be calculated for 95% confidence.

	
Worsening of Stroke is determined as the number of participants experiencing at least one worsening of stroke divided by the number of participants observed over the 90-day period in that treatment group, between RNS60 and placebo control participants. This will be modeled using generalized linear modeling assuming a binary distribution with sandwich estimation, where observations are nested by site. Because superiority over placebo and lower dose is hypothesized, testing will reflect this superiority framework with one-tailed tests.

10 SUPPORTING DOCUMENTATION and OPERATIONAL CONSIDERATIONS

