2 STUDY OVERVIEW

2.1 Study Objectives

2.1.1 *Primary Objective*

The primary objective is to determine the safety of RNS60 in adult subjects (aged 18 years or older) with large vessel occlusion (LVO) and acute ischemic stroke (AIS) based on serious adverse events (SAEs) and 90-day mortality. To be eligible for this trial, subjects must have sudden onset of focal neurological symptoms within 24 hours prior to randomization consistent with an ischemic stroke. Symptoms must be persistent and present at the time of enrollment.

2.1.2 *Secondary Objectives*

The secondary objectives are to evaluate the efficacy of RNS60 in the following outcomes:

1. Reducing global disability (as measured using the Modified Rankin Scale [mRS] at 90 days)
2. Decrease in infarct volume (as defined by imaging at 48 hours)
3. Improving neurological outcome (as measured using the National Institutes of Health Stroke Scale [NIHSS] at 24 hours)
4. Reducing worsening of stroke, defined as progression, or hemorrhagic transformation, of the index stroke as documented by medical imaging that results in:
 - (a) a life-threatening situation requiring intervention, and/or
 - (b) increased disability as determined by a ≥ 4 -point increase from lowest NIHSS pre decline, and/or
 - (c) death by 48 hours or during hospital admission.
5. Reducing functional dependence (as defined by mean Barthel Index (BI) at Day 90)
6. Improving health-related quality of life, as measured by the EuroQol health-related quality of life (EQ-5D-5L) at Day 90

These outcomes will be assessed in the following hierarchical order (to control for the overall Type I error rate): first between high-dose RNS60 (1.0 mL/kg/h RNS60) compared to placebo, then both low and high dose RNS60 combined compared to placebo, and then between low-dose RNS60 (0.5 mL/kg/h RNS60) compared to placebo. In the analyses of efficacy, the combined-dose inference will be done within the statistical models by averaging the results in the two active doses and comparing to placebo. (This is in contrast to performing a separate

analysis in which subjects on active dose are treated as a single treatment arm.) The exception to this approach is the non-parametric analysis in Section 3.4.4.1, where the data in the two active arms are combined into a single group to be compared to placebo.

2.1.3 *Attributes of the Estimands*

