The attributes of the main estimand (target of estimation), used for the primary analysis of the highest ranked efficacy endpoint (modified Rankin Scale (mRS) score) are defined below. Although the primary objective of this study is related to safety, analysis of the efficacy endpoints (secondary objectives of the study) will be based on a pre-defined hierarchy and therefore, an estimand is defined.

- The **population** is defined as the intent-to-treat study population (see Section 3.2.3).
- The corresponding **variable** to be obtained for each subject required to address the scientific question is disability based on the mRS score at Day 90. The mRS will be evaluated as a binary outcome (0-2, 3-6).
- The **population level summary** considered in this study is the odds ratio between RNS60 1.0 mL/kg/h and placebo 1.0 mL/kg/h.
- The **treatments** to be compared are RNS60 1.0 mL/kg/h and placebo 1.0 mL/kg/h. The treatments will be compared according to the randomized groups, regardless of the treatment that was actually received. In accordance with the treatment policy principle, all available data will be used in the analysis, regardless of e.g., premature discontinuation of study medication or administration of any concomitant treatment.
- The **intercurrent events** (ICEs) considered as potentially impacting results and/or interpretation are:
 - Premature discontinuation of study treatment
 - Death
 - Coronavirus Disease 2019 (COVID-19) pandemic related events (assessments that were missed due to COVID-19).

For the data that are missing due to premature discontinuation of study treatment, an assumption of Missing At Random (MAR) will be made. Sensitivity analyses will be conducted using an assumption of Missing Not At Random (MNAR). No specific imputation will be done for these missing data, because the likelihood-based analysis approach can manage subjects with incomplete data under the assumption of MAR.

For the data that are missing due to COVID-19, an assumption of MAR will be made for all analyses, both primary and sensitivity analyses.

For the mRS, NIHSS and BI endpoints death is included as part of the scoring, so no imputation of these endpoints is required for subjects who die. Similarly, for the worsening of stroke endpoint, death represents a worsening. For the infarct progression end point, death will be represented by a missing value.

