The NIHSS is a standardized neurological examination scale that is a valid and reliable measure of disability and recovery after acute stroke. The NIHSS assessment is a standardized 15-item impairment scale, intended to evaluate neurologic outcome and degrees of recovery for subjects with stroke. The scale assesses levels of consciousness, extraocular movements, visual fields, facial muscle function, extremity strength, sensory function, coordination (ataxia), language (aphasia), speech (dysarthria), and hemi-inattention (neglect). The NIHSS will be administered at baseline, post-EVT (2h), 24h, 48h, Day 6 (or discharge), Day 30 and Day 90. The NIHSS will only be scored by those trained in the use of this scale.

Table 3. Scales and score range in NIHSS

| Item | Scales | Score range |
|------|----------------------------|-------------|
| 1a | Level of Consciousness | 0-3 |
| 1b | LOC Questions | 0-2 |
| 1c | LOC Commands | 0-2 |
| 2 | Best Gaze | 0-2 |
| 3 | Visual | 0-3 |
| 4 | Facial Palsy | 0-3 |
| 5a | Motor Arm –Left Arm | 0-4 |
| 5b | Motor Arm –Right Arm | 0-4 |
| 6a | Motor Leg –Left Leg | 0-4 |
| 6b | Motor Leg – Right Leg | 0-4 |
| 7 | Limb Ataxia | 0-2 |
| 8 | Sensory | 0-2 |
| 9 | Best Language | 0-3 |
| 10 | Dysarthria | 0-2 |
| 11 | Extinction and Inattention | 0-2 |

Scoring:

Each item is scored in the respective ranges listed in Table 3 (0-2, 0-3, or 0-4), and untestable items are scored as "UN". A score of 0 indicates normal performance. Total scores on the NIHSS range from 0-42, with higher values reflecting increasing severity.

Stroke severity is further stratified in the following way (Brott, Adams, Olinger, Marler, Barsan, Biller, & Hertzberg, 1989):

> 25: Very severe

15-24: Severe

5-14: Mild to moderately severe

< 5: Mild

The predictive value of the scale can also aid in planning a subject's rehabilitation or long-term care needs as early as on the day of admission. NIHSS scores can be

interpreted in the following way (Schlegel, D., Kolb, S. J., Luciano, J. M., Tovar, J. M., Cucchiara, B. L., Liebeskind, D. S., & Kasner S. E., 2003):

≥ 14 – Severe: Long-term care in nursing facility required

6-13 – adequate: Acute inpatient rehabilitation required

≤ 5 – Mild: 80% with this score are discharged home

4) The proportion of study subjects with worsening of stroke at the 90-day study period.

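### Worsening of stroke is a 90-day endpoint in the protocol and SAP 2.3.2(4), but SAP 3.4.2(4) tests it over 48 hours or the hospital stay, and SAP 6.4 does not declare the change

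*SAP*

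**What the plan says.** The protocol's objective is simply "Reducing worsening of stroke" and gives no period. Its outcome (3.2.2) is "The proportion of patients with worsening of stroke over the 90-day study period". Its analysis (9.3.3) takes the participants with at least one worsening, "divided by the number of participants observed over the 90-day period in that treatment group".

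The SAP is not consistent with itself. Section 2.3.2(4) lists the endpoint as "The proportion of study subjects with worsening of stroke at the 90-day study period". Section 3.4.2(4) is headed "The proportion of subjects with worsening of stroke over the 48-hours/duration of admission" and goes on: "The simple effect of treatment on worsening stroke at 48 hours/admission duration will be examined". Objective 2.1.2(4) words its death limb as "death by 48 hours or during hospital admission". The estimand section, 2.1.3, says that "for the worsening of stroke endpoint, death represents a worsening" and sets no time limit.

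**The concern.** A binary endpoint is not defined until its observation period is. Which patients count as events, and how many, depends on which SAP section is followed. Take a patient who goes home and then has an imaging-documented progression that meets one of the three severity limbs. That patient is an event over 90 days and a non-event over the admission.

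The admission reading has a further weakness. Observation lasts as long as the hospital stay, so two patients with the same underlying risk are watched for different lengths of time. If the arms differ in length of stay for any reason, they can differ in counted events with no difference in the rate of worsening.

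The endpoint sits in a fixed testing order, so its definition also affects whether the ranks below it are read as confirmatory or exploratory.

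**Working it through.** The plan states no event rate, effect size or power for this endpoint, so there is no figure to reproduce. The check is mainly a comparison of texts.

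| Place | Period for worsening of stroke |
|---|---|
| Protocol 3.1.2, objective | none given |
| Protocol 3.2.2, outcome | 90 days |
| Protocol 8.1.9, definition | no end of observation; the reference NIHSS is the lowest in hospital |
| Protocol 9.3.3, analysis | 90 days |
| SAP 2.1.2(4), objective | 48 hours or admission, on the death limb |
| SAP 2.1.3, estimand | death counts; no period |
| SAP 2.3.2(4), endpoint list | 90 days |
| SAP 3.4.2(4), heading and tested effect | 48 hours / admission |

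**Precedence.** SAP sections 1 and 6.4 let the SAP override the protocol. That cannot settle a conflict between SAP 2.3.2(4) and SAP 3.4.2(4).

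**The slash.** It gives no rule for choosing between 48 hours and the admission. With the 90 days of 2.3.2(4), there are three candidate windows.

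**Time at risk.** The model in 3.4.2(4) adjusts for age, baseline NIHSS, ASPECTS, log baseline infarct volume, perfusion status, occlusion location and site. Nothing represents length of observation.

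**Death.** SAP 3.1.7 assigns an NIHSS of 42 at every scheduled visit after death. SAP 3.4.2(4) identifies cases partly by a rise of at least 4 points, worst minus best NIHSS, with no visit limit. Since 42 − 38 = 4, any patient whose best score was 38 or lower meets the rise by dying, whatever the cause and whether or not imaging showed progression.

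**Weight of one patient.** 100 / 3 ≈ 33 per arm, and 1 / 33 = 3.0 percentage points.

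**Scale, on assumed rates only.** Let P48 be the risk in the first 48 hours (assumed 5% to 15%) and L the risk from day 2 to day 90 (assumed 5% to 10%). With constant late hazard, P(T) = 1 − (1 − P48)(1 − L)^((T − 2)/88).

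- 90 days against 48 hours: the difference is (1 − P48) × L. Its lowest value is 0.85 × 0.05 = 4.25 points (33 × 0.0425 = 1.4 events per arm). Its highest is 0.95 × 0.10 = 9.5 points (3.1 events).
- Same hazard in both arms, different stays, P48 = L = 10%: 5 days gives 10.3%, 7 days 10.5% and 20 days 11.9%.
- Early-weighted late hazard, with half of H = −ln(1 − L) falling in days 2 to 14: P(T) = 1 − (1 − P48) × exp(−h), where h = 0.5H × min(T − 2, 12)/12 + 0.5H × max(T − 14, 0)/76. With P48 = 5% and L = 10%, 5 days gives 6.2% and 20 days 10.2%.
- Over the whole grid, a deliberately wide contrast of 5 against 20 days produces 0.7 to 4.0 points, or 0.2 to 1.3 events per 33, with no drug effect.

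**Deaths.** SAP 2.2.4 anticipates 10% stroke deaths, or 3.3 per arm of 33. If 25% to 75% of them came after discharge (assumed), 33 × 0.10 × 0.25 = 0.8 to 33 × 0.10 × 0.75 = 2.5 deaths per arm could count over 90 days but not over the admission.

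**The case against.** SAP 3.4.2 says that each endpoint's primary time point is the one defined in its own subsection, and that other applicable time points are compared as exploratory. On that reading 3.4.2(4) sets the tested window and a 90-day comparison may still be run. This has some force, but it does not say which side of the slash applies, and it makes the protocol's own outcome exploratory without saying so.

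SAP 6.4 excepts the further defining of endpoints from its statement that nothing significant has changed. Moving from 90 days to 48 hours or the admission is more than further definition, and 2.3.2(4) still says 90 days.

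Protocol 8.1.9 takes the lowest NIHSS from the hospital stay, which gives some support to an in-hospital endpoint. But it fixes the reference score and says nothing of when observation ends.

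Three stronger readings are tempting, and the documents do not support them:

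- A reader might infer that the test fails to answer the stated objective. SAP 2.1.2(4) itself carries the 48-hour or admission wording, on its death limb, and the protocol objective has no window.
- A reader might infer that fluid overload lengthens stay and so biases rank 4. Placebo is infused at the same 1.0 mL/kg/h as the high dose, so the planned volume is equal. A volume effect on stay could enter only through the low-dose arm (ranks 9 and 14), and the documents link overload to stopping the infusion, not to longer stay.
- A reader might infer that every hemorrhagic transformation after discharge is reclassified. It counts only if it is life-threatening and requires intervention, raises the NIHSS by at least 4 points, or results in death.

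The endpoint is also secondary and unpowered, and rank 4 is confirmatory only if ranks 1 to 3 succeed. That limits the weight of the point.

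**Conclusion.** The contradiction is established from the text and needs no assumption. The tested window matches neither the protocol's outcome and analysis nor SAP 2.3.2(4), is itself ambiguous, and is not declared in SAP 6.4. Under the admission reading it is also tied to a post-randomization event plausibly linked to recovery; a strict 48-hour window is free of that defect.

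The direction and size of any bias cannot be derived. The illustrative figures rest wholly on assumed rates and lengths of stay. They suggest that the choice between 48 hours and 90 days matters more (about 1.4 to 3.1 events per arm) than differential stay does (about 1.3 at most). This should be corrected, but it does not undermine the trial's primary safety aim.

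**What to change.** Before unblinding:

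- State one fixed window for every patient in SAP 2.1.2(4), 2.3.2(4) and 3.4.2(4): infusion start to Day 90, matching the protocol. Keep a fixed 0-48 h version as a supportive analysis.
- If the sponsor prefers a shorter primary window, make it a fixed number of hours or days, not the admission, and list it in SAP 6.4 as a change from the protocol.
- Restrict the NIHSS, adverse event and death data to the chosen window.
- Bring SAP 2.1.3 and the case-identification rule into line with the definition: imaging-documented progression or hemorrhagic transformation plus one of the three limbs. The NIHSS of 42 assigned after death should not by itself create an event.

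The cost is SAP wording and a revised derivation, with no new data collection. Adverse events, mortality, NIHSS at Days 30 and 90, and brain imaging up to Day 90 are already planned.

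The downside is weaker ascertainment of late events. Telephone contacts give no NIHSS, the only scheduled MRI after 48 hours is at Day 90, and the SAP's version history says stroke-related death is not collected as a separate category. Late events will therefore rest partly on adverse event, imaging and death records, and the SAP should say how they are classified.

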3.1.7 Handling of Death

Subjects who die during the study will be scored as follows for all scheduled visits following the death: 6 for mRS, 42 for NIHSS and 0 for BI. The value 6 for mRS is part of the mRS definition. The values for NIHSS and BI are conventions, consistent with the worst possible score.

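### The rule that identifies worsening of stroke uses an unordered NIHSS range, so recovery can be counted as worsening

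*SAP*

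**What the plan says.** SAP 3.4.2 (4) first gives a definition. There must be progression or hemorrhagic transformation "of the index stroke as documented by medical imaging and that is (a) life-threatening requiring intervention and/or (b") there is at least a "4-point increase from lowest NIHSS pre decline and/or (c) results in death". So imaging governs all three limbs, the limbs are alternatives, and the NIHSS limb runs forward in time from a low point. SAP 2.3.2 (4) repeats this. Protocol 3.1.2 and 8.1.9 agree in substance, although 8.1.9 takes the lowest score during the hospital stay.

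The following sentence in SAP 3.4.2 (4) states how subjects are to be found in the data: at least a "4-point increase in their worst minus best NIHSS score and adverse events status (life threatening requiring intervention or death) as collected in the CRFs".

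Two related matters are stated inconsistently:

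- **Death.** SAP 2.1.3 says that "for the worsening of stroke endpoint, death represents a worsening", with no imaging condition. SAP 3.1.7 assigns "6 for mRS, 42 for NIHSS and 0 for BI" at scheduled visits after death. The definition counts only deaths that result from documented progression or transformation.
- **Window.** The analysis heading in SAP 3.4.2 is "The proportion of subjects with worsening of stroke over the 48-hours/duration of admission", and SAP 2.1.2 (4) has "death by 48 hours or during hospital admission". SAP 2.3.2 (4) has "The proportion of study subjects with worsening of stroke at the 90-day study period", and Protocol 3.2.2 and 9.3.3 also use 90 days.

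**The concern.** Worst minus best is never negative and does not depend on which score came first. Most patients who do well after thrombectomy show a large difference because the later scores are lower. The rule as written also leaves open whether *and* means that both conditions are needed or that either is enough, whether the baseline score counts, and whether imaging still applies.

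The endpoint ranks 4th, 9th and 14th in the SAP's secondary hierarchy, and Protocol 9.3.3 intends the efficacy results to supply effect sizes for a later trial. If recovery is flagged as worsening, a drug that aids recovery looks harmful on this endpoint. If a life-threatening or fatal adverse event is required, deteriorations of 4 or more points without such an event are missed. Two programmers could derive different endpoints from the same data. The primary safety endpoints, SAEs and 90-day mortality, do not depend on this rule.

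**Working it through.** The documents give no event rate or effect size for this endpoint, so there is no figure of the plan's own to reproduce.

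**1. The two rules on the same NIHSS paths.** Range = maximum − minimum. Ordered rise = largest value of (score − lowest earlier score). The threshold for both is 4.

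| Path | Range | Ordered rise |
|---|---|---|
| 16-12-9-7-5 (steady recovery) | 11, flagged | −2, not flagged |
| 16-8-6-14-14 (true decline) | 10, flagged | 8, flagged |
| 16-14-14-42-42 (death scored 42) | 28, flagged | 28, flagged |

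Protocol 5.1 requires a baseline NIHSS above 5, that is at least 6. If baseline counts, anyone who recovers to 2 or less has a range of at least 4. Leaving baseline out does not cure this: post-baseline scores of 10-8-6-4 still give a range of 6.

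**2. Three ways to program the sentence.** Assumed inputs, none from the documents:

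- w = true worsening: placebo 0.10, drug 0.06. The true odds ratio is (0.06/0.94)/(0.10/0.90) = 0.57.
- q = improvement of 4 or more points among the others: placebo 0.50, drug 0.65.

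*A. NIHSS criterion sufficient, imaging not applied.* Flagged = w + (1−w)q.
- Placebo: 0.10 + 0.90×0.50 = 0.550. Drug: 0.06 + 0.94×0.65 = 0.671. Odds ratio 1.67.
- Over w from 0.05 to 0.15 and q from 0.3 to 0.7, 34% to 75% of patients are flagged, and 63% to 93% of the flags are false.

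*B. NIHSS criterion sufficient, imaging applied.* Let g be the share of non-worseners with imaging progression or transformation, assumed equal in both arms and independent of improvement. Flagged = w + (1−w)gq.
- g = 0.1: 0.145 vs 0.121, odds ratio 0.81.
- g = 0.2: 0.190 vs 0.182, odds ratio 0.95.
- g = 0.4: 0.280 vs 0.304, odds ratio 1.13.
- Reversal starts at g = 0.04/(0.94×0.65 − 0.90×0.50) = 0.248.

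*C. A life-threatening or fatal adverse event is also required.* Let b be the share of true worseners who qualify by the NIHSS limb alone, and d the share of non-worseners who meet both conditions. Flagged = w(1−b) + (1−w)d.
- b = 0.3, d = 0: 0.070 vs 0.042, odds ratio 0.58.
- b = 0.7, d = 0.10: 0.120 vs 0.112, odds ratio 0.92.
- There is no reversal, but a share b of true events (30% to 70%) is missed.

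**3. What 33 patients per arm would show.** The target is 100 patients in three equal arms. The exact binomial probability that the observed proportion is higher on drug is 20% with correct coding, 81% under A, and 40% (g = 0.2) to 53% (g = 0.4) under B.

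**4. Simulated NIHSS paths under A.** Assumptions: baseline uniform on 6–25, five assessments to Day 6, mean recovery of 20–60% of the deficit, visit noise SD 0.5–1.5, and a true decline in 5–15% of patients. The range rule flags 44–94% with baseline and 29–83% without it. The ordered rule flags 4–26%. With mean recovery of 50% on drug against 30% on placebo, noise SD 1.0 and 10% true decline in both arms, the range rule with baseline gives an odds ratio of 2.85 and the ordered rule 0.79.

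**5. Death.** A death inside the window is scored 42, so any earlier in-window NIHSS of 38 or less meets the 4-point criterion, whatever the cause of death. The definition would count that death only if it resulted from imaging-documented progression or transformation.

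**The case against.** The best defence is that the definition governs and the next sentence only names the data sources: NIHSS for one limb, adverse events for the other two. The sentence speaks of an increase, so *best* could mean the low point before the decline and *worst* the later score. SAP 6.4 also says that nothing significant changed apart from specifying analyses and further defining endpoints. That may well be what was intended. But the sentence says how subjects will be identified, and the version history lists a change to this subsection to designate them. In a SAP that overrides the protocol, the literal rule has no time order. The intended meaning has to be read into it.

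Several limits on the size of the problem do stand:

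- The example under A depends on the assumed gain in recovery. At 50% vs 55% the odds ratio is 1.12 and the 81% becomes 54%. With equal recovery of 50% the odds ratio is 0.92, so the effect is diluted but not reversed.
- Reversal under B needs imaging progression to be independent of improvement. If improvement is half as frequent among patients with progression, the odds ratios at g = 0.1, 0.2 and 0.4 are 0.71, 0.81 and 0.95.
- The distortion runs against the drug. The trial is not powered, and a non-significant result higher in the hierarchy makes this comparison exploratory.
- The window mismatch is a separate inconsistency. It is included because the same sentence cannot be programmed without settling it.
- The derivation could be set out in the separate programming specifications, and hemorrhage reads in the Imaging Charter. Neither document is available here. The redacted SAS code is not held against the plan.

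**Conclusion.** The concern holds. The identification sentence does not implement the definition that precedes it, and each of the three literal ways to apply it departs from that definition: A and B can count recovery as worsening, and C removes the NIHSS limb as an independent route. This follows from the text and needs no assumed rates.

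The size does rest on assumptions. In the illustration, a true odds ratio of 0.57 becomes 1.67 under A, 0.81 to 1.13 under B, and 0.58 to 0.92 under C with 30% to 70% of true events missed. Reversal is therefore possible but not certain; attenuation is the more general result. This should be fixed before unblinding. It affects a ranked secondary endpoint and the estimates carried into a later trial, not the primary safety conclusions.

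**What to change.** Replace the identification sentence in SAP 3.4.2 (4) with a derivation that states:

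1. The NIHSS limb is met if any score in the window is at least 4 points above the lowest score at an earlier assessment, baseline included.
2. Imaging-documented progression or hemorrhagic transformation of the index stroke is required for all three limbs.
3. The limbs are joined by *or*.
4. Either every death in the window counts, as SAP 2.1.3 implies, or only deaths meeting limb (c). Say also whether the NIHSS of 42 assigned in SAP 3.1.7 may trigger the NIHSS limb.
5. One window applies, reconciling 48 hours/admission (SAP 2.1.2 and 3.4.2) with 90 days (SAP 2.3.2, Protocol 3.2.2 and 9.3.3). Align the reference score in Protocol 8.1.9 with item 1.

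The cost is SAP wording and derivation code. NIHSS by visit, adverse events and brain imaging are already collected. Before unblinding, confirm that progression and hemorrhagic transformation are recorded in a usable form: the core-lab reads named in Protocol 10.2.2 are ASPECTS, TICI and infarct growth, with no hemorrhage read mentioned. If they are not recorded elsewhere, a blinded read of the stored scans would be needed.
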